3.3.1 Injection with the needle-free (NF) system

The device used for needle free system was **Comfort-in™** (Mika Medical Global Co, Busan, Korea) anesthesia device (Figure 1). The **Comfort-in™ system**, has a micro-hole injection needle (0.15 mm) that injects the anesthetic solution under the mucosa. The pressure can be controlled according to the dose of the drug to be used, thereby reduced the pain that may occur with the needle in the injection. Before the injection procedure, the children were demonstrated the popping sound produced by device to prevent reflex reactions, and they informed that they would feel as if their gum were punched. The NF injection device was prepared according to the manufacturer's instructions, placed in full contact with the buccal mucosa and a pre-withdrawn dose of 0.1 ml was applied to the buccal region for topical purposes by the pushing the top of the device. After 10-15 seconds, the same procedure was repeated with withdrawn dose of 0.3 ml. After 5 min the treatment commenced, and the children were instructed to raise their hand if they experienced pain during the procedure. Each time the child indicated pain, in accordance with the same protocol an additional 0.3 ml of anesthetic solution was administered, until the sufficient anesthetic effect was obtained and the final amount of anesthetic solution

The Effect of Needle-free Injection System on Dental Injection Pain in Children: A Cross-over, Randomized Clinical Trial

were recorded. Precautions were taken to prevent tissue ballooning. After the treatment, duration of the analgesia effect (min) were also recorded. The presence of post-operative pain in patients was assessed via a phone call 1 day after the procedure.

3.3.2 Injection with the traditional method (TM)

The TM was used with traditional syringe on the opposite side of the dental arch. The injection site was dried with a cotton-tip applicator, and topical anesthetic spray (Lidocaine 10%, Vemcain, Turkey) was applied to the injection area with cotton-tip for 1-2 min. The traditional injection was performed with a 26-gauge, 40-mm, disposable syringe with a needle (Genject, Turkey). The depth of penetration was only a few millimeters and 0.3ml of anesthetic solution was deposited. After 5 min the treatment commenced, and the children were instructed to raise their hand if they experienced pain during the procedure. Each time the child indicated pain, in accordance with the same protocol an additional 0.3 ml of anesthetic solution was administered, until the sufficient anesthetic effect was obtained and the final amount of anesthetic solution were recorded. Precautions were taken to prevent tissue ballooning. After the treatment, duration of the analgesia effect (min) were also recorded. The presence of post-operative pain in patients was assessed via a phone call 1 day after the procedure.

Both NF and TM anesthesia techniques were performed with 4% articaine hydrochloride with 1/100,00 epinephrine (Ultracaine D-S forte, Hoechst Canada Inc., Montreal Quebec, Canada) as an anesthetic agent.

3.3.3 Subjective assessment

Pain levels were subjectively evaluated using the Wong-Baker Faces Pain Rating Scale (WB PRS) (Wong DL, 1988), which measures the unpleasantness or affective dimension of a child's pain experience. The PRS consists of a set of cartoon faces with varying facial expressions ranging from a smile/laughter to tears, and each child is asked to select the facial expression that best represents his/her experience of discomfort. Each face has a numerical value ranging from 0 (smiling face, 'no hurt') to 5 (crying/screaming face, 'hurts worst'). This scale was explained to the children carefully in advance. Immediately after the each injection, the children were asked to rate the level of pain perceived during the administration, using the PRS.

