3.4 Data collection

A structured form was designed to collect information regarding

- (1) patient's age;
- (2) gender;
- (3) type of teeth injected
- (4) type of dental treatment (filling or pulpotomy);
- (5) total amount of local anesthetics (LAs) used (ml)
- (6) duration of the analgesia effect (min)
- (7) post-op pain (after one day)
- (8) score on WB PRS after injection
- (9) score on FLACC during injection.

The Effect of Needle-free Injection System on Dental Injection Pain in Children: A Cross-over, Randomized Clinical Trial

Statistical Analysis

Post hoc power analysis was conducted for the study and the results of the comparison between the injection systems and Wong Baker scores were evaluated. According to this, with a total data set of 28 individuals, consisting of two independent groups and two dependent measurements, the power of the study was found to be 0.94 according to the G*Power 3.9.1.4 program, based on the partial eta squared (η^2) value of 0.108 obtained with a 0.05 error margin from the repeated measures ANOVA. The data were statistically analyzed using SPSS software (version 15.0, SPSS). Paired t-tests or Wilcoxon nonparametric tests were used to compare data within groups over two time periods, according to check the distribution whether normally distributed or not. The Chi-square test (X^2 -test) was also used to compare discrete random variables. Spearman's Rho correlation coefficient was used to find any relationship between two continuous variables. A p-value ≤ 0.05 was considered statistically significant.

4. Results

Total of 28 children, consisting of 18 girls (64.3%) and 10 boys (35.7%) aged 6–12 years were involved in this study. Mean age was 8.07 years with a standard deviation of 1.41 years. At the end of this study, a total of 56 injections were obtained for 28 children as NF injection (n = 28) and TM injection (n = 28).

In the study, when the distributions of the parameters (gender, type of dental treatment, type of teeth, and post-operative pain) were evaluated according to the type of injection technique, it was found that there was no statistically significant difference between the groups. (Table 1)

Table 1. Distribution of injection techniques based on evaluation parameters

Variables		Needle Free (NF) n	Traditional Method (TM) n	Total	p
Gender	Girl	18	18	36	1,000
	Boy	10	10	20	
Type of dental treatment	Filling	22	14	36	0,051
	Pulpotomy	6	14	20	
Type of teeth injected	1 st primary molar	12	7	19	0,259

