	2 nd primary molar	16	21	37	
Post-op pain (after one day)	Pain	5	7	12	0,746
	No pain	23	21	44	

*The Chi-square test (X^2 -test) was also used to compare discrete random variables.

Accordingly Table 2, in the group that received Needle-Free anesthesia in the first session and Traditional Method in the second session, the Wong-Baker scores were 4.44 ± 3.28 and 1.55 ± 0.88 , respectively. On the other hand, in the group that received Traditional Method anesthesia in the first session, the WB score was 1.68 ± 1.91 , while in the Needle-Free anesthesia group, the WB score was 2.52 ± 2.56 . In both cases, regardless of the method of anesthesia applied first, no statistically significant difference was found in the two groups. In the FLACC scores, for the Traditional Method - Needle Free group significant change was observed ($p = 0.025$) while for the Needle Free- Traditional Method group no statistically significant difference was observed ($p=0.141$). There were significant differences in the Amount of Anesthetic Solution (ml) and Duration of the Analgesia Effect (min) between the first and second visits for both injection methods, respectively as $p=0.003$ for NF-TM and $p<0.0001$ for

The Effect of Needle-free Injection System on Dental Injection Pain in Children: A Cross-over, Randomized Clinical Trial

TM-NF groups. The amount of anesthetic solution used for the 1st visit NF injection was $0,91\pm 0,48$ ml and $0,65\pm 0,30$ ml was for the 2nd visit NF injection. These amounts were statistically lower than TM injection in both visits. In the first visit, the mean duration of the analgesia effect in the NF group was 85.00 ± 39.05 min, whereas in the second visit, the mean duration for NF injection was found to be 90.26 ± 43.25 min. In the TM group, the mean anesthesia duration for the first and second visits was 140.00 ± 59.97 min and 130.00 ± 50.74 min, respectively. Regardless of the visit in which it was first applied, the duration of the analgesia effect in the NF group was found to be statistically significantly shorter than in the TM group ($p < 0,001$).

Table 2: Comparison of the 1st visit and 2nd visit measurements for continuous random variables in Needle Free-Traditional Method and Traditional Method - Needle Free

	1 st visit	2 nd visit	p
Wong Baker (WB) Scores			
Needle Free-Traditional Method	4,44±3,28	1,55±0,88	0,056
Traditional Method - Needle Free	1,68±1,91	2,52±2,56	0,119
FLAAC			

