Needle Free-Traditional Method	0,78±1,09	0,11±0,33	0,141
Traditional Method - Needle Free	0,21±0,41	0,68±0,67	0,025
Amount of Anesthetic Solution (ml)			
Needle Free-Traditional Method	0,91±0,48	1,62±0,38	0,003
Traditional Method - Needle Free	1,37±0,42	0,65±0,30	<0,0001
Duration of the Analgesia Effect (min)			
Needle Free-Traditional Method	85,00±39,05	130,00±50,74	0,001
Traditional Method - Needle Free	140,00±59,97	90,26±43,25	<0,001

*paired t-test was used

*Needle Free-Traditional Method group: 1st visit Needle Free and 2nd visit Traditional Method was used of injection.

*Traditional Method - Needle Free group: 1st visit Traditional Method and 2nd visit Needle Free was used of injection

Table 3: Wong-Baker and FLACC Scores in Needle Free-Traditional Method and Traditional Method - Needle Free groups based on gender

	Gender	Needle Free-Traditional Method Group		p	Gender	Traditional Method-Needle Free Group		p
		1 st visit Needle Free	2 nd visit Traditional Method			1 st visit Traditional Method	2 nd visit Needle Free	
Wong Baker	Girl N=6	4.1, (1.5-8.5)	2, (0-2)	0,141	Girl N=12	2, (0.5-2)	1, (0-3.5)	0,558
	Boy N=3	4.1, (2-4)	2, (2-2)	0,18	Boy N=7	0, (0-4)	2, (2-4)	0,059
FLACC	Girl N=6	0, (0-1.5)	0, (0-0.25)	0,414	Girl N=12	0, (0-0)	0.5, (0-1)	0,053
	Boy N=3	1, (0-1)	0, (0-0)	0,180	Boy N=7	0, (0-1)	1, (0-1)	0,317

*Wilcoxon nonparametric test was used

*Needle Free-Traditional Method group: 1st visit Needle Free and 2nd visit Traditional Method was used for injection.

*Traditional Method - Needle Free group: 1st visit Traditional Method and 2nd visit Needle Free was used for injection

* The values are presented as Median, (Inter Quartile Range)

In our study, which used a crossover design, we evaluated the effect of gender differences on Wong-Baker and FLACC scores for needle-free and traditional method injections administered

The Effect of Needle-free Injection System on Dental Injection Pain in Children: A Cross-over, Randomized Clinical Trial

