		1 st visit Needle Free	2 nd visit Traditional Method			1 st visit Traditional Method	2 nd visit Needle Free	
Amount of Anesthetic Solution (ml)	Filling-Filling N=4	0.65, (0.325-1.125)	1.3, (1.05-1.85)	0,068	Filling-Filling N=8	1.1, (1-1.85)	0.55, (0.325-0.9)	0,012
	Filling-Pulpotomy N=3	0.9, (0.3-0.9)	2, (1.5-2)	0,180	Filling-Pulpotomy N=2	1.4, (1.3-1.4)	1, (1-1)	0,180
	Pulpotomy-Filling N=2	1.35, (1.2-1.35)	1.75, (1.5-1.75)	0,180	Pulpotomy-Filling N=9	1.5, (1.1-1.85)	0.6, (0.3-0.9)	0,008

*Wilcoxon nonparametric test was used

*Needle Free-Traditional Method group: 1st visit Needle Free and 2nd visit Traditional Method was used for injection.

*Traditional Method - Needle Free group: 1st visit Traditional Method and 2nd visit Needle Free was used for injection

*The values are presented as Median, (Inter Quartile Range)

*filling-filling group: 1st visit filling and 2nd visit filling restoration have been done

*filling-pulpotomy group: 1st visit filling and 2nd visit pulpotomy restoration have been done

*pulpotomy-filling group: 1st visit pulpotomy and 2nd visit filling restoration have been done

Table 5 showed the evaluation whether the type and sequence of different restorations administered in different sequences over two sessions with needle-free and traditional method

10.04.2017

The Effect of Needle-free Injection System on Dental Injection Pain in Children: A Cross-over, Randomized Clinical Trial

injections resulted in any differences in the amount of anesthetic solution used. The results indicated a significant difference in the amount of anesthetic solution used in the group that received TM injection in the first session and NF injection in the second session, the group that received filling in both the first and second sessions, and the group that received pulpotomy in the first session and filling in the second session. A significantly lower amount of anesthetic solution was used in the NF injection in both groups (Table 5).

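### Section 3.3.3 puts Wong-Baker on 0 to 5, but the reported scores are impossible on that scale and fit 0, 2, 4, 6, 8, 10; two medians and 12 small-cell upper quartiles in Tables 3 to 5 are also wrong

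*Combined protocol and SAP*

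**What the plan says.** Section 3.3.3 defines the Wong-Baker score by "Each face has a numerical value ranging from 0 (smiling face, 'no hurt') to 5 (crying/screaming face, 'hurts worst".

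Section 4 (text on Table 2) reports, for the sequence NF then traditional method (TM), that "the Wong-Baker scores were 4.44 ± 3.28 and 1.55 ± 0.88". For NF at the second visit of the TM-NF sequence it reports that "the WB score was 2.52 ± 2.56". Table 3 gives the sequence sizes: 6 + 3 = 9 for NF-TM and 12 + 7 = 19 for TM-NF.

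Tables 3 to 5 carry the footnote "The values are presented as Median, (Inter Quartile Range". The entries that matter most here are, as median (lower to upper quartile):

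- Table 3, Wong-Baker, NF in the NF-TM sequence: girls N=6, 4.1 (1.5 to 8.5); boys N=3, 4.1 (2 to 4).
- Table 4, Wong-Baker, NF: filling-filling N=4, 7 (3 to 9.5); filling-pulpotomy N=3, 4 (2 to 4); pulpotomy-filling N=2, 1 (0 to 1). In the TM-NF sequence, filling-filling N=8 is 2 (0.5 to 5.5).

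The Statistical Analysis section rests its power statement on this outcome: "the power of the study was found to be 0.94 according to the G*Power 3.9.1.4 program".

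**The concern.** Several printed Wong-Baker values exceed the stated maximum of 5, so the definition and the results cannot both be right. A reader who trusts 3.3.3 would judge the level of pain, and the difference between techniques, to be twice as large relative to the scale as they are. FLACC is on 0 to 10 (section 3.3.4), so the two measures are also easily miscompared.

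The subgroup tables raise a second doubt. A median of 4.1 cannot arise from three or six whole-number scores, and the boys' 4.1 lies above its own upper quartile. In many cells of two or three children the upper quartile simply repeats the median, which understates the upper end of the data, mostly for NF.

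**Working it through.** **1. The printed mean and SD cannot be reproduced on 0 to 5.** For a fixed total, the SD is largest when the scores sit at the two ends.

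- NF, n=9, mean 4.44: the total must be 40 (40/9 = 4.444). The extreme set is one 0 and eight 5s. SD = √[(200 − 40²/9)/8] = √2.778 = **1.67**. Printed: 3.28.
- NF, n=19, mean 2.52: the total must be 48 (48/19 = 2.526, printed truncated). The extreme set is nine 5s, one 3 and nine 0s. SD = √[(234 − 48²/19)/18] = √6.263 = **2.50**. Printed: 2.56.

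**2. They can be reproduced on 0, 2, …, 10.** A search of all whole scores from 0 to 10, odd values allowed, used the Table 4 medians and quartiles with the Table 2 mean and SD. Quartiles followed the (n+1)p rule, and the upper quartile was not used in cells of two or three. For NF at visit 1 of the NF-TM sequence there is one solution: {2,6,8,10}, {2,4,6}, {0,2}. Total 40, sum of squares 264, mean 4.444, SD = √[(264 − 177.78)/8] = 3.283, against 4.44 and 3.28 printed. Every value is even. The TM scores of the same children are also unique: {0,2,2,2}, {0,2,2}, {2,2}. The two TM-NF score sets can be rebuilt from even scores as well; odd values were not searched there.

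**3. N=3 upper quartiles, Tables 4 and 5.** With four ordered values and (n+1)p quartiles, x1 + x4 = (Q1 + Q3 − 0.5 × median)/0.75 and x2 + x3 = 2 × median. Subtracting the N=4 and N=2 cell totals from the Table 2 total leaves the N=3 cell (NF, NF-TM sequence):

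| Measure | Total of 9 | N=4 total | N=2 total | N=3 total | Printed lower quartile + median | Third value |
|---|---|---|---|---|---|---|
| Wong-Baker | 40 | 12 + 14 = 26 | 2 | 12 | 2 + 4 | **6** |
| FLACC | 7 | 3 + 1 = 4 | 0 | 3 | 0 + 1 | **2** |
| Amount (ml) | 8.2 | 1.5 + 1.3 = 2.8 | 2.7 | 2.7 | 0.3 + 0.9 | **1.5** |

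Under (n+1)p the upper quartile of three values is the largest, so it should be 6, 2 and 1.5. Printed: 4, 1 and 0.9. The rebuilt sets also match Table 2: FLACC 0.778 and 1.093 (0.78, 1.09); amount 0.911 and 0.483 (0.91, 0.48). Replacing the third value by the printed quartile gives 4.22 and 3.23 for Wong-Baker and 0.844 and 0.430 for amount, which do not match.

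**4. The 4.1 medians and the boys' cells, Table 3.** Five ways of drawing three boys from the nine rebuilt scores keep the girls' quartiles at 1.5 and 8.5. The boys' TM scores are {2,2,2}. The asymptotic Wilcoxon p must equal the printed 0.18:

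| Boys, NF | Differences | p |
|---|---|---|
| {2,2,4} | 0, 0, 2 | 0.317 |
| {2,2,6} | 0, 0, 4 | 0.317 |
| {2,6,6} | 0, 4, 4 | 0.157 |
| {4,6,6} | 2, 4, 4 | 0.102 |
| **{2,4,6}** | 0, 2, 4 | **0.180** |

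For {2,4,6}: zero dropped, z = 1.5/√1.25 = 1.342, p = 0.180. For {4,6,6}: z = 3/√3.375 = 1.633, p = 0.102. So the boys are {2,4,6} and the girls {0,2,2,6,8,10}, with median 4 in both. The boys' upper quartile is 6, not 4. The FLACC split is unique: boys {0,1,2}, upper quartile 2, printed 1.

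That makes five N=3 cells: two in Table 3, two in Table 4, one in Table 5.

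**5. N=2 cells.** The median is the midpoint of two values. If the lower quartile is below it, the values differ, and the upper quartile must lie above it under (n+1)p or linear interpolation. Seven cells break this: 1 (0 to 1) twice, 0.5 (0 to 0.5) twice, 1.35 (1.2 to 1.35), 1.75 (1.5 to 1.75) and 1.4 (1.3 to 1.4). Total 7 + 5 = **12**, of which nine are NF cells.

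**6. What the scale does and does not change.** NF minus TM is (40 + 48 − 14 − 32)/28 = 1.5 points over all children, or (26/9 + 16/19)/2 = 1.87 as the unweighted mean of the sequences. That is 30 to 37% of a 0 to 5 range but 15 to 19% of 0 to 10. Multiplying every score by two leaves p-values, correlations and eta squared unchanged. The power figure also reproduces: f² = 0.108/0.892 = 0.1211, λ = 0.1211 × 28 × 2/0.5 = 13.56 (correlation 0.5 assumed), F with 1 and 26 df, power 0.943.

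**The case against.** Four points can be made on the other side.

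- *The quartile corrections depend on a rule the documents do not name.* This is partly right. A closest-observation rule returns 4 as the upper quartile of {2,4,6}, as printed, and a rule that interpolates at n × p returns 1 for {0,2}, as printed. But at N=4 both return an observed score, so neither can give 9.5 from whole scores. Linear interpolation fits no set of four whole scores from 0 to 10 to 3, 7 and 9.5, whereas (n+1)p fits exactly one. The N=3 corrections remain inferences from reconstruction, a step less direct than the N=2 cells.
- *Boys {2,2,4} would make their printed quartiles correct.* True on quartiles alone, but the printed p of 0.18 rules it out. In the Table 4 Wong-Baker filling-pulpotomy cell the p-value does not separate {2,4,6} from {2,4,4}; there the Table 2 mean and SD decide.
- *Twelve separate misprints are unlikely.* Agreed. In 21 of the 22 cells with N=2 or 3 the upper quartile equals the median, and in the other it is 4 against 4.1. That points to one systematic cause. In the ten small cells not counted, such as 2 (0 to 2), equality can be correct.
- *The impact is small.* A reader of Table 4 soon meets 7 and 9.5, no Wong-Baker threshold is set, no conclusion rests on the small-cell quartiles, and nothing suggests mixed coding. This limits the severity. It does not excuse an incorrect definition of the child-reported pain outcome.

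**Conclusion.** The concern holds. The 0 to 5 definition in section 3.3.3 is incompatible with the reported scores; this follows from the printed values alone. The coding 0, 2, 4, 6, 8, 10 is established for the nine NF-TM children and is consistent with the other 19.

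Both 4.1 medians are impossible and rebuild as 4. Twelve upper quartiles are wrong: seven from the two-value arithmetic, and five by reconstruction under the (n+1)p rule that the larger cells fit.

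The main consequence is interpretation: pain and the technique difference read as twice their true share of the scale. The tests and the power figure stand, provided one coding applied to every child. This should be corrected, but it does not overturn the analysis.

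**What to change.** 1. Check the data forms and state in 3.3.3 the face values actually recorded.
2. Confirm that the same coding applies to all 28 children. Re-run the Wong-Baker analyses only if it does not.
3. Correct both 4.1 medians in Table 3 from the source data.
4. Recompute the quartiles in Tables 3 to 5 with one named rule. For cells of two or three children, show the individual values or the minimum and maximum instead.

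The cost is a check of the forms, one sentence in 3.3.3 and corrected table entries. No re-analysis is needed if a single coding was used.

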3.3.4 Objective assessment

Pain level also objectively evaluated by the operator using the Face, Legs, Activity, Cry, Consolability (FLACC) Scale. (Merkel SI, 1997) This scale includes the following points: face, leg, activity, cry and consolability. Each one of these five categories records either 0, 1, or 2 which result in either a minimum degree of 0 or a maximum degree of 10. According to this scale: 0 = quiet and relaxed (no pain), 1-3 = mild discomfort or pain, 4-6 = moderate pain, and 7-10 = severe pain.

3.4 Data collection

A structured form was designed to collect information regarding

- (1) patient's age;
- (2) gender;
- (3) type of teeth injected
- (4) type of dental treatment (filling or pulpotomy);
- (5) total amount of local anesthetics (LAs) used (ml)
- (6) duration of the analgesia effect (min)
- (7) post-op pain (after one day)
- (8) score on WB PRS after injection
- (9) score on FLACC during injection.

The Effect of Needle-free Injection System on Dental Injection Pain in Children: A Cross-over, Randomized Clinical Trial

Statistical Analysis

Post hoc power analysis was conducted for the study and the results of the comparison between the injection systems and Wong Baker scores were evaluated. According to this, with a total data set of 28 individuals, consisting of two independent groups and two dependent measurements, the power of the study was found to be 0.94 according to the G*Power 3.9.1.4 program, based on the partial eta squared (η^2) value of 0.108 obtained with a 0.05 error margin from the repeated measures ANOVA. The data were statistically analyzed using SPSS software (version 15.0, SPSS). Paired t-tests or Wilcoxon nonparametric tests were used to compare data within groups over two time periods, according to check the distribution whether normally distributed or not. The Chi-square test (X^2 -test) was also used to compare discrete random variables. Spearman's Rho correlation coefficient was used to find any relationship between two continuous variables. A p-value ≤ 0.05 was considered statistically significant.

4. Results

Total of 28 children, consisting of 18 girls (64.3%) and 10 boys (35.7%) aged 6–12 years were involved in this study. Mean age was 8.07 years with a standard deviation of 1.41 years. At the end of this study, a total of 56 injections were obtained for 28 children as NF injection (n = 28) and TM injection (n = 28).

In the study, when the distributions of the parameters (gender, type of dental treatment, type of teeth, and post-operative pain) were evaluated according to the type of injection technique, it was found that there was no statistically significant difference between the groups. (Table 1)

Table 1. Distribution of injection techniques based on evaluation parameters

Variables		Needle Free (NF) n	Traditional Method (TM) n	Total	p
Gender	Girl	18	18	36	1,000
	Boy	10	10	20	
Type of dental treatment	Filling	22	14	36	0,051
	Pulpotomy	6	14	20	
Type of teeth injected	1 st primary molar	12	7	19	0,259
	2 nd primary molar	16	21	37	
Post-op pain (after one day)	Pain	5	7	12	0,746
	No pain	23	21	44	

*The Chi-square test (X^2 -test) was also used to compare discrete random variables.

Accordingly Table 2, in the group that received Needle-Free anesthesia in the first session and Traditional Method in the second session, the Wong-Baker scores were 4.44 ± 3.28 and 1.55 ± 0.88 , respectively. On the other hand, in the group that received Traditional Method anesthesia in the first session, the WB score was 1.68 ± 1.91 , while in the Needle-Free anesthesia group, the WB score was 2.52 ± 2.56 . In both cases, regardless of the method of anesthesia applied first, no statistically significant difference was found in the two groups. In the FLACC scores, for the Traditional Method - Needle Free group significant change was observed ($p = 0.025$) while for the Needle Free- Traditional Method group no statistically significant difference was observed ($p=0.141$). There were significant differences in the Amount of Anesthetic Solution (ml) and Duration of the Analgesia Effect (min) between the first and second visits for both injection methods, respectively as $p=0.003$ for NF-TM and $p<0.0001$ for

The Effect of Needle-free Injection System on Dental Injection Pain in Children: A Cross-over, Randomized Clinical Trial

TM-NF groups. The amount of anesthetic solution used for the 1st visit NF injection was $0,91\pm 0,48$ ml and $0,65\pm 0,30$ ml was for the 2nd visit NF injection. These amounts were statistically lower than TM injection in both visits. In the first visit, the mean duration of the analgesia effect in the NF group was 85.00 ± 39.05 min, whereas in the second visit, the mean duration for NF injection was found to be 90.26 ± 43.25 min. In the TM group, the mean anesthesia duration for the first and second visits was 140.00 ± 59.97 min and 130.00 ± 50.74 min, respectively. Regardless of the visit in which it was first applied, the duration of the analgesia effect in the NF group was found to be statistically significantly shorter than in the TM group ($p < 0,001$).

Table 2: Comparison of the 1st visit and 2nd visit measurements for continuous random variables in Needle Free-Traditional Method and Traditional Method - Needle Free

	1 st visit	2 nd visit	p
Wong Baker (WB) Scores			
Needle Free-Traditional Method	4,44±3,28	1,55±0,88	0,056
Traditional Method - Needle Free	1,68±1,91	2,52±2,56	0,119
FLAAC			
Needle Free-Traditional Method	0,78±1,09	0,11±0,33	0,141
Traditional Method - Needle Free	0,21±0,41	0,68±0,67	0,025
Amount of Anesthetic Solution (ml)			
Needle Free-Traditional Method	0,91±0,48	1,62±0,38	0,003
Traditional Method - Needle Free	1,37±0,42	0,65±0,30	<0,0001
Duration of the Analgesia Effect (min)			
Needle Free-Traditional Method	85,00±39,05	130,00±50,74	0,001
Traditional Method - Needle Free	140,00±59,97	90,26±43,25	<0,001

*paired t-test was used

*Needle Free-Traditional Method group: 1st visit Needle Free and 2nd visit Traditional Method was used of injection.

*Traditional Method - Needle Free group: 1st visit Traditional Method and 2nd visit Needle Free was used of injection

Table 3: Wong-Baker and FLACC Scores in Needle Free-Traditional Method and Traditional Method - Needle Free groups based on gender

	Gender	Needle Free-Traditional Method Group		p	Gender	Traditional Method-Needle Free Group		p
		1 st visit Needle Free	2 nd visit Traditional Method			1 st visit Traditional Method	2 nd visit Needle Free	
Wong Baker	Girl N=6	4.1, (1.5-8.5)	2, (0-2)	0,141	Girl N=12	2, (0.5-2)	1, (0-3.5)	0,558
	Boy N=3	4.1, (2-4)	2, (2-2)	0,18	Boy N=7	0, (0-4)	2, (2-4)	0,059
FLACC	Girl N=6	0, (0-1.5)	0, (0-0.25)	0,414	Girl N=12	0, (0-0)	0.5, (0-1)	0,053
	Boy N=3	1, (0-1)	0, (0-0)	0,180	Boy N=7	0, (0-1)	1, (0-1)	0,317

*Wilcoxon nonparametric test was used

*Needle Free-Traditional Method group: 1st visit Needle Free and 2nd visit Traditional Method was used for injection.

*Traditional Method - Needle Free group: 1st visit Traditional Method and 2nd visit Needle Free was used for injection

* The values are presented as Median, (Inter Quartile Range)

In our study, which used a crossover design, we evaluated the effect of gender differences on Wong-Baker and FLACC scores for needle-free and traditional method injections administered

The Effect of Needle-free Injection System on Dental Injection Pain in Children: A Cross-over, Randomized Clinical Trial

in different sequences over two sessions. The analysis showed no statistically significant differences between the groups (Table 3). Similarly, present study evaluated the impact of the type and sequence of restorations (filling-filling, filling-pulpotomy, pulpotomy -filling) on Wong-Baker and FLACC scores for needle-free and traditional method injections administered in different sequences over two sessions. Results demonstrated that there were no statistically significant differences between the groups (Table 4).

Table 4: Wong-Baker and FLACC Scores in Needle Free-Traditional Method and Traditional Method - Needle Free groups based on type of dental treatment

	Type of Dental Treatment	Needle Free-Traditional Method Group		p	Type of Dental Treatment	Traditional Method-Needle Free Group		p
		1 st visit Needle Free	2 nd visit Traditional Method			1 st visit Traditional Method	2 nd visit Needle Free	
Wong Baker	Filling-Filling N=4	7, (3-9.5)	2, (0.5-2)	0,109	Filling-Filling N=8	2, (0.5-2)	2, (0.5-5.5)	0,167
	Filling-Pulpotomy N=3	4, (2-4)	2, (0-2)	0,180	Filling-Pulpotomy N=2	0, (0-0)	1, (0-1)	0,317
	Pulpotomy-Filling N=2	1, (0-1)	2, (2-2)	0,317	Pulpotomy-Filling N=9	2, (0-3)	2, (0-4)	0,655
FLACC	Filling-Filling N=4	0.5, (0-2.5)	0, (0-0)	0,180	Filling-Filling N=8	0, (0-0)	1, (0-1)	0,096
	Filling-Pulpotomy N=3	1, (0-1)	0, (0-0)	0,180	Filling-Pulpotomy N=2	0, (0-0)	0.5, (0-0.5)	0,317
	Pulpotomy-Filling N=2	0, (0-0)	0.5, (0-0.5)	0,317	Pulpotomy-Filling N=9	0, (0-1)	1, (0-1)	0,257

*Wilcoxon nonparametric test was used

*Needle Free-Traditional Method group: 1st visit Needle Free and 2nd visit Traditional Method was used for injection.

*Traditional Method - Needle Free group: 1st visit Traditional Method and 2nd visit Needle Free was used for injection

*The values are presented as Median, (Inter Quartile Range)

*filling-filling group: 1st visit filling and 2nd visit filling restoration have been done

*filling-pulpotomy group: 1st visit filling and 2nd visit pulpotomy restoration have been done

*pulpotomy-filling group: 1st visit pulpotomy and 2nd visit filling restoration have been done

Table 5. Amount of Anesthetic Solution (ml) in Needle Free-Traditional Method and Traditional Method - Needle Free groups based on type of dental treatment

	Type of Dental Treatment	Needle Free-Traditional Method Group		p	Type of Dental Treatment	Traditional Method-Needle Free Group		p
		1 st visit Needle Free	2 nd visit Traditional Method			1 st visit Traditional Method	2 nd visit Needle Free	
Amount of Anesthetic Solution (ml)	Filling-Filling N=4	0.65, (0.325-1.125)	1.3, (1.05-1.85)	0,068	Filling-Filling N=8	1.1, (1-1.85)	0.55, (0.325-0.9)	0,012
	Filling-Pulpotomy N=3	0.9, (0.3-0.9)	2, (1.5-2)	0,180	Filling-Pulpotomy N=2	1.4, (1.3-1.4)	1, (1-1)	0,180
	Pulpotomy-Filling N=2	1.35, (1.2-1.35)	1.75, (1.5-1.75)	0,180	Pulpotomy-Filling N=9	1.5, (1.1-1.85)	0.6, (0.3-0.9)	0,008

*Wilcoxon nonparametric test was used

*Needle Free-Traditional Method group: 1st visit Needle Free and 2nd visit Traditional Method was used for injection.

*Traditional Method - Needle Free group: 1st visit Traditional Method and 2nd visit Needle Free was used for injection

*The values are presented as Median, (Inter Quartile Range)

*filling-filling group: 1st visit filling and 2nd visit filling restoration have been done

*filling-pulpotomy group: 1st visit filling and 2nd visit pulpotomy restoration have been done

*pulpotomy-filling group: 1st visit pulpotomy and 2nd visit filling restoration have been done

Table 5 showed the evaluation whether the type and sequence of different restorations administered in different sequences over two sessions with needle-free and traditional method

10.04.2017

The Effect of Needle-free Injection System on Dental Injection Pain in Children: A Cross-over, Randomized Clinical Trial

injections resulted in any differences in the amount of anesthetic solution used. The results indicated a significant difference in the amount of anesthetic solution used in the group that received TM injection in the first session and NF injection in the second session, the group that received filling in both the first and second sessions, and the group that received pulpotomy in the first session and filling in the second session. A significantly lower amount of anesthetic solution was used in the NF injection in both groups (Table 5).

According to Spearman's Rho correlation coefficient test, no correlation was found between age and Wong Baker, FLACC scores, and the amount of anesthetic solution administered respectively ($p=0,830$, $p=0,436$, $p=0,976$). Similarly, no correlation was found between Wong Baker scores and the amount of anesthetic solution administered ($p=0,537$) and Wong Baker scores and the duration of the analgesia effect ($p=0,468$). However, a negative correlation was found between the FLACC score and the amount of anesthetic solution ($p=0,033$). Moreover a positive correlation was found between the FLACC score and Wong Baker scores as well as between the amount of dose administered and duration of analgesia effect respectively ($p=0,000$, $p=0,009$).
